6.4 Immobilization and Patient Positioning

Positioning of the patient for daily radiotherapy will be disease site and patient specific. Devices such as alpha-cradles, aquaplast and vac-lock treatment bags will be utilized to ensure daily reproducibility of set-up between 5-8 mm. Isocenter marks will be made on the patient and immobilization device; treatment table position and source to skin distance (SSD) will be noted for each patient and used daily for patient set-up.

6.5 Simulation and Treatment Planning

Simulation will consist of orthogonal simulation radiographs and CT scan in the treatment position or CT simulation on a CT simulator. These CT images and other imaging modalities (MRI) are transferred to a treatment-planning computer and undergo co-registration (image fusion) to define the treatment planning study set. Outlines of normal tissues and target volumes are created on axial, sagittal coronal, or any arbitrary plane within the study set. All targets and structures must define a three dimensional polygon and follow the target volume conventions previously (GTV, CTV and PTV) or describe a specific normal tissue structure. Normal tissues contoured may include (but are not limited to) the epiphysis, physis, metaphysis, cortical bone including long or flat bone, and individual muscle groups.

Treatment plans will be generated by a cooperative effort between medical physics and the responsible radiation oncologist. Brachytherapy catheter placement will follow the guidelines described by MSKCC (11). The most appropriate set of treatment beams, dose constraints or source activities will be evaluated for three-dimensional conformal, IMRT and brachytherapy treatment plans respectively. Plans will be evaluated subjectively by review of isodose distributions and objectively by review of dose-volume histograms. The most appropriate plan will be selected by weighing the benefits and complexities of target coverage, normal tissue sparing, dose heterogeneity and complexity of delivery. Guidelines for these parameters are as follows:

- 6.5.1 Target coverage 95% of the PTV should be covered by 95% of the prescribed dose (note PTV excludes the contained CTV, i.e. PTV-CTV). In the case of brachytherapy treatment plans 100% of the CTV must receive 95% of the prescribed dose.
- 6.5.2 Normal tissue doses Normal tissues should be treated to as low a dose as possible while maintaining adequate target coverage. Exceptions to mandating complete target coverage should be made in the case of critical structures such as spinal cord (limited to 4500-5000 cGy), large volumes of bowel (limited to 4500 cGy), excessive volume of lung, etc.

- 6.5.3 Dose heterogeneity For 3-D conformal and IMRT treatment plans no more than 15% of the combined GTV, CTV and PTV volume may exceed 115% of the prescribed dose. For brachytherapy plans dose heterogeneity is anticipated and dose to 5% of the target volume (CTV) will be recorded.
- 6.5.4 Treatment plan complexity As treatment plans allow more conformal delivery of radiation to complex target volumes, delivery times and delivery complexity will increase. No objective criteria exist for judging treatment plan complexity, but a less complex plan may be preferable if consistent and reliable delivery is better achieved.
- 6.6 Treatment Delivery

Following completion of treatment planning, the patient will return and undergo verification of position and individual treatment beams. After correct localization of the patient on the treatment couch, radiation therapy will commence. All fields are treated daily at the prescribed dose and fractionation scheme outlined in tables 6.3.1, 6.3.2, and 6.3.3. Localization images are obtained weekly or more often for accuracy of patient positioning. For brachytherapy treatments, following treatment planning, radioactive sources are ordered and catheter placement is again verified, either clinically or radiographically if indicated.

- 6.7 Treatment Related Effects of Radiation
 - 6.7.1 Radiotherapy related treatment effects are both location- and timedependent and clearly related to the dose delivered to specific organs or structures. Effects are divided into acute reactions, early delayed reactions and late reactions divided by arbitrary time periods indicated below.
 - 6.7.2 Acute reactions (during radiotherapy): Hair loss, errythema of skin, desquamation, edema of soft tissues,
 - 6.7.3 Subacute reactions (6 weeks to 3 months after irradiation): Soft tissue edema
 - 6.7.4 Late reactions (more than 3 months after irradiation): Fibrosis of soft tissues including muscle, injury to muscle or bone, including changes in bone growth, and changes in tissue vascularity.
- 7.0 Pretreatment Evaluations

Pretreatment evaluations consist of examinations of physical function, and imaging studies. These studies will also be obtained during and following completion of delivery of radiation (table 5.1, 7.1). Imaging studies obtained pretreatment and during the follow-up period are designed to concur with national and institutional studies.

7.1 Evaluations of Physical Function

Analytic evaluations of physical function will be obtained in conjunction with the departments of physical and occupational therapy as well as consultation with orthopedic surgery. Evaluations will be made post surgery and prior to irradiation for patients undergoing external beam radiotherapy. For patients who will

receive brachytherapy with or without external beam irradiation an additional evaluation will be obtained prior to surgery. General information regarding height (sitting and standing), weight, and limb length or muscle bulk will be obtained, as relevant. All evaluations use quantitative subjective scales or absolute measurements and include the contralateral unirradiated side if relevant. Assessments are sequential in nature to develop data regarding the time course of specific treatment related effects. Specific instruments of physical function are included in appendix C. The scope of such evaluations will include information regarding range of motion, muscle tone and strength specific to the muscle groups and joints to be irradiated.

- 7.2 Diagnostic Imaging
 - 7.2.1 Magnetic Resonance Imaging

Magnetic resonance imaging beyond the standard of care (RTSARC MRI) will no longer be used in the trial in new patients or those currently on study. The section below will be left in place as a reference for the patient data collected prior to this amendment.

Magnetic resonance imaging (MR) will be used for all patients enrolled on study unless implanted metallic objects preclude its use in which case a diagnostic CT study will be used. The specific MRI sequences required for this protocol are outlined in appendix D and are appended on to the site specific MR imaging protocol. Dynamic contrast enhanced MR (DCE-MR) has been applied to evaluate tumor response and necrosis in patients with osteosarcoma. This technique delineates rate of contrast leakage for specified regions of tissue, which provides imaging based objective measurements of microvascular changes in both adjacent normal tissue and intact tumor (if present). Arterial spin labeling also evaluated vascular flow and density in sites were it is applicable. Both DCE-MR and arterial spin labeling MR will be applied when feasible though certain anatomic sites such and chest wall may not be imaged with these techniques due to the effects of motion and technical limitations of the sequence

Anatomic measurements of the primary tumor, muscle volume, bone length, cortical thickness and physis closure will be made with multi-slice axial coronal and sagital imaging acquired with the typical clinical sequences (e.g T1 fat saturation VIBE, Flash,or MPR Rage techniques). Tumor measurements will be made using a unidimensional maximal diameter. All measurements, including those of bone length, volume, muscle volume and quantitative MR parameters will be obtained following post imaging processing of MR datasets at the time of analysis.

7.2.2 Positron Emission Tomography (PET)

PET imaging beyond the standard of care will no longer be used in this trial in new patients or those currently on study. The section below will be left in place as a reference for the patient data collected prior to this amendment.

PET scans will be obtained of the whole body following administration of 18F-Fluorodeoxyglucose (FDG) per standard imaging protocols. PET-FDG evaluates glucose uptake (and most often its metabolism) into tissues. This form of functional imaging is becoming more prevalent and

its application to pediatric oncology is promising. Currently, little data exist regarding the application of PET to pediatric patients with musculoskeletal tumors. Following surgical resection PET may better define the region at high risk for residual disease prior to radiation. In intact tumors PET obtained serially before and after radiation may define functional radiotherapeutic response and its clinical significance.

Normal tissue imaging with PET has usually occurred in the brain when functional neuro-imaging studies are desired. Extracranial assessment of normal (non-tumor) tissues is not well studied. PET-FDG may provide information about normal tissue metabolism following radiation.

A PET-FDG requires the administration of radioactive labeled glucose. The amount of radiation given for one PET scan is about one-third of the yearly limit for radiation workers (physicians, nurses, scientists) over the course of one year. Four PET scans are scheduled during this study. These imaging studies are encouraged but optional. The PET-FDG studies are optional; the patient or their guardian may decline any or all PET imaging studies.

7.2.3 QCT Bone Densitometry

Bone densitometry will be obtained using QCT at years 7 or 8, 10 or 11 of follow-up and at age 18 (if year 10 is earlier). This study may be performed at the same time as a QCT obtained to document / investigate bone loss due to systemic therapy. The entire treated bone or bone adjacent the treatment site will be identified and imaged in its entirety. This will allow assessment of bone density within and outside the high dose radiation regions (hypothesized to alter bone density). Correlations will be made between bone density and radiation dose. There may be limits of applying the QCT technique to whole bone imaging outside of long bones. Complex bony structures such as the face may have limited applicability of this technique, while adjacent bones such as vertebral bodies would be more appropriate. In these cases the P.I. will review the patient's initial dosimetry from their radiation therapy treatment plan and consult with [name] or her designee regarding the use of QCT.

The axial images of the entire bone will also be utilized to assess bone growth over the 10-year follow-up period and into adulthood (18 years of age) compared with the initial study MR and / or CT simulation study. Models of long-term bone growth will be generated based on this data.

QCT studies inherently deliver a small dose to the patient in order to obtain density information regarding the bone. Typical QCT studies would image one or more lumbar vertebral bodies or a portion of a long bone, but not the entire bone. For this study we are requiring the entire bone to be imaged to fully study the effects of radiation on these bones, including understanding its effect on growth, correlation with risk of fracture due to decreased bone density, as well as overall bone health. This could entail imaging the radius, a vertebral body, rib or tibia. All of the sites would have potentially different effective radiation exposures for the patient. Though there is some clinical benefit to this procedure, we obtained radiation phantom base dose estimates (in conjunction with [name], Radiation Oncology Physics faculty and [name], Diagnostic Imaging Physics) for a number of possible scenarios in order to better assess the risk-benefit ratio to the patient. This information is attached in appendix E. In brief, imaging of the upper arm, which would also likely expose a portion of the thorax, would result in the highest exposure to the patient. Our phantom measurements of a 10 year old and adult aged patient yielded exposures of 2.2 and 2.3 mSv respectively. This is significantly lower (by 67% and 72%) than our typical exposures from diagnostic quality scan protocols (yielding 7.5 and 9 mSv, respectively).

8.0 Evaluations During the Follow-up Period

These studies are identical to the pretreatment evaluations. The timing of these evaluations is outlined in table 8.1 for all patients. Imaging studies obtained pretreatment and during the follow-up period are designed to concur with national and institutional studies. Exceptions to the below schedule will be made at the discretion of the principal investigator. Table B2 (appendix B) indicates which studies are considered "standard of care" and which are for research purposes only.

Table 8.1

Evaluation following initiation of Radiation Therapy for All Patients

Evaluation	Мо	nths	afte	er Init	iation	of Ra	dia	tion ⁻	Ther	apy*		@18 years
	3	6	9	12	18	24	36	48	60	84/96		of age
Clinical Physical Examination	x	x	x	x	x	x	x	x	x	x		x
PT/OT												
Functional Evaluation	X	X	X	X	X	X	X	X	X	x	X	X
Site Specific Functional Scales	-		-	-	-	-	-	-	-	X	X	X
Diagnostic Imaging												
QCT	-	-	-	-	-	-	-	-	-	x	x	x

* Exceptions to the evaluation scheme will be made at the discretion of the principal investigator when clinical or logistical considerations preclude protocol-timely evaluation. Patients that are not seen at the 84 month time point will be evaluated at the following year's clinical visit (approximately 96 and 132 months).

9.0 Toxicity Monitoring

Toxicity will be monitored and graded at each visit for the musculoskeletal system and the bone, joint, skin and subcutaneous tissue sections of the late radiation morbidity scoring system according to the NCI Common Toxicity Criteria v2.0. Toxicity grades will be determined by the treating radiation oncologist at each follow-up evaluation utilizing the pertinent patient history, physical exam and imaging studies to assess grades.

9.1 Reporting Adverse Experiences and Deaths

Principal investigators are responsible for promptly reporting to the IRB any adverse events that are unanticipated, serious, and that may represent potential harm or increased risk to research participants. When an unanticipated death occurs, the PI should report it to the Director of the Office of Human Subjects' Protection immediately,

A reportable event entry into TRACKS should follow within 48 hours. Serious, unanticipated, and related or possibly related events must be reported within 10 working days. At the same time, the investigator will notify the study sponsor (NIH or pharmaceutical company), cooperative group, and/or the FDA, as appropriate. To report adverse events in gene therapy trials, investigators should use specific RAC forms found at

http://www4.od.nih.gov/oba/RAC/Adverse_Event_Template.doc .

The principal investigator is responsible for reviewing the aggregate toxicity reports and reporting to the IRB if the frequency or severity of serious toxicities exceed those expected as defined in the protocol or based on clinical experience or the published literature. Any proposed changes in the consent form or research procedures resulting from the report are to be prepared by the study team and submitted with the report to the IRB for approval.

The following definitions apply:

A serious event refers to any event in which the outcome is fatal or lifethreatening, results in permanent disability, causes inpatient hospitalization or prolongs existing inpatient hospitalization, or is a congenital anomaly, cancer, or overdose.

An unanticipated adverse event refers to those not identified in their nature, severity, or frequency in the current risk documents (e.g., investigator's brochure), or consistent with the investigational plan.

The following are considered reportable: Any injuries, serious event or other unanticipated adverse events involving risk to participants or others which occur at a frequency above that considered acceptable by the investigators and the IRB. (FDA) As described in 4.3 above, the OHSP Director or designee performs the initial review of unanticipated problems or serious adverse event reports. Internal reports of events that are unanticipated, serious, and related or possibly related to study interventions or procedures are then forwarded to the IRB Chair or designee and if necessary, referred to the full IRB. Based on the frequency and seriousness of adverse events, the IRB Chair or Committee may deem it necessary to suspend or terminate a research study or studies.

10.0 Criteria for Response, Treatment Failure and Sites of Failure

Response to local therapy will be evaluated by history, physical exam and imaging studies as indicated in table 8.1. Additional evaluations will be at the discretion of the treating physicians as warranted by the clinical situation. Response will be determined serially prior to radiation therapy and at each follow-up evaluation. The designation of response is measured relative to initial imaging and physical examination for the current course of treatment (i.e. imaging at diagnosis or imaging at recurrence prompting treatment on this study).

10.1 Local Failure – Tumor recurrence or progressive disease by imaging or biopsy that falls within the original clinical target volume (CTV) is classified as a local failure counting as an event against tumor control. This can be accomplished by comparing the location of the recurrence by image fusion or direct measurement with the image guided radiotherapy target volumes. Patients that have a positive biopsy at the primary tumor site will be classified as a local failure only if the positive biopsy results in a change in therapy or change in patient status

(additional local or systemic therapy). Treatment failures are classified according to the location of the recurrent tumor relative to the targeted volumes (PTV, CTV and GTV) diagrammed in appendix A.

- 10.2 Complete Response Disappearance of all primary and regional tumor as defined by physical examination and imaging. Patients undergoing complete resection prior to radiation or patients with no visible tumor on baseline imaging prior to radiation are considered a complete response at the time of irradiation.
- 10.3 Partial Response More than 50% reduction in the unidimensional maximal diameter of the tumor compared with the baseline evaluation.
- 10.4 Stable Disease Less than 50% reduction in the unidimensional maximal diameter of the tumor compared with the baseline evaluation.
- 10.5 Progressive Disease More than 25 % increase in the unidimensional maximal diameter of the tumor compared with the baseline evaluation. In patients that have undergone complete resection prior to radiation, progressive disease is the appearance of any new local disease. Appearance of new regional or metastatic disease or a 25% increase in regional or metastatic disease will be classified as regional or metastatic progression. Any positive biopsy of a known metastatic disease site that results in a change in therapy or change in patient status (e.g. additional local or systemic therapy) will be classified as disease progression

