2.5.1 Primary Objectives

Patients with MST will have their target volumes (GTV, CTV and PTV) defined on planning imaging studies with anatomic and geometric margins defined in section 6.3. Target definitions are consistent with active national protocol guidelines when available. Radiation doses are prescribed relative to the PTV and are also consistent with available national protocol guidelines. Local tumor control will be evaluated by clinical exam and imaging studies as defined in section 10.1. Local control rates with image guided radiation therapy will be compared with expected rates of control using traditional techniques for patients with Ewing's sarcoma, resected soft tissue sarcoma and clinical group III rhabdomyosarcoma. Patients with rhabdomyosarcoma and nonrhabdomyosarcoma soft tissue sarcoma will have further reductions (by 5mm) in their clinical target volume (CTV) margins to remain consistent with national protocols. This group of patients will be monitored separately as well as together with the prior group of patients with RMS and STS for rates of local failure. This plan is outlined in statistical section 12.1. Local control and local/regional patterns of failure will be determined relative to the GTV, CTV, PTV, the volume irradiated to the prescription dose as noted in section 10.6 and primary site imaging parameters. The center or apparent origin of the recurrence will be considered when assigning a pattern of failure (appendix A).

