6.3.1.3 Brachytherapy (limited to use in soft tissue Ewing's family of tumors)

GTV1b – The surgical tumor bed defined by intraoperative examination and preoperative imaging studies

CTV1b – This target volume consists of GTV1 with a 1 cm lateral margin and a 2 cm proximal and distal margin relative to the long axis of the tumor for interstitial approaches. For intracavitary and surface brachytherapy applications a margin appropriate for the tumor site and presentation, usually 1-2 cm is recommended.

No PTV exists for brachytherapy procedures.

- 6.3.2 Rhabdomyosarcoma and small round blue cell undifferentiated sarcoma
 - 6.3.2.1 Definitive radiotherapy (no surgical resection)

GTV1 – Visible gross tumor including initially involved soft tissue prior to biopsy or therapy as defined by physical exam and imaging studies.

CTV1 – This target volume consists of GTV1 with a 1 cm anatomic margin of tissue, respecting anatomic barriers of

tumor spread, and regional areas of nodal involvement warranting irradiation.

PTV1 – This volume includes the CTV1 with a treatment site and immobilization device specific margin for target motion and daily treatment set-up variation, usually 5 - 10mm.

PTV2 – This volume includes the GTV1 with a treatment site and immobilization device specific margin for target motion and daily treatment set-up variation, usually 5 - 10mm.

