The Second Phase Accrual: The original plan of accrual of 110 patients has been completed (September 2007), and additional accrual of patients is planned for this study as the second phase of accrual. The numbers of patients anticipated for the four treatment groups for the second phase accrual are shown in Table 12.1.4. These numbers are estimated based on the accrual of an additional 100 patients with the same distribution of disease (histology, size and use of surgery) as the initial 110 patient cases. For the groups of ESFT-small/resected and ESFT-large, the treatments in the second phase are exactly the same as that in the first phase, so the patients in the second phase will be taking together with those in the first phase for safety monitoring according to the plan in Table 12.1.3. The treatments for the groups of Group III RMS and Resected STS will be changed such that the irradiation margin will be decreased from 2cm to 1.5cm for the Group III RMS, and be decreased from 1.5cm to 1.0cm for the Resected STS. Since the patients in the second phase in these two groups may be at higher risk for local failure than those in the first phase (due to clinical treatment margin reduction), these patients will be monitored separately from, as well as together with, the patients from the first phase. The monitoring plans for these two groups are given in Table 12.1.5. For each group, the accrual of patients will be held if the stopping rule is activated by any one of the two monitoring plans for the aroup.

Table 12.1.4	
The Second Phase Accrual in Groups for Local Control Analysis	

	Group III RMS	Resected STS	Resected ESFT or Small (<8cm) ESFT	Large (≥8cm) ESFT
W & w/o Metastases	35	35	13	12

For Group III RMS or for the Resected or Small ESFT (target 85%), the 5% lower limit for non-sequential tests for the local control rate is 26 (74.3%) or 50 (76.9%), respectively, for the final accrual of 35 or 65 patients. For the Resected STS (target rate 90%), the 5% lower limit is 28 (80.0%) or 54 (83.1%), respectively, for the final accrual of 35 or 65 patients. From the sample sizes of the fixed sample test design, we derived the sequential boundaries in Table 12.1.5 for monitoring the local control rates.

Table 12.1.5

The Second Phase Safety Monitoring Plan: Minimum number of patients locally controlled per patients enrolled in each treatment group*

	Minimum Expected Number of Patients with Local Tumor Control					

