Appendix A.

Classification of tumor recurrence based on imaging may be classified into one of three categories: 1) in-volume, 2) out-of-volume or 3) indeterminate. Tumor recurrences classified as out-of-volume must clearly fall outside the planning target volume (PTV). Those failures that fall fully within the gross tumor or clinical target volumes (GTV and CTV) are classified as in-volume failures. All other failures are marginal in nature and will be analyzed based on their geometric center of origin and percent volume within the target volumes. A failure that intersects the GTV or CTV is classified as a local failure and counts as an event against local control.

The image below provides a graphical representation of potential patterns of failure.

Indeterminate

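### Local failure is tied to each patient's own CTV, which is 5 mm narrower in the second phase for Group III RMS and Resected STS, so any bias favours no loss of control; its size is unknown and the part due to the cut is limited

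*Combined protocol and SAP*

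**What the plan says.** **Event definition.** Section 10.1: "Tumor recurrence or progressive disease by imaging or biopsy that falls within the original clinical target volume (CTV) is classified as a local failure". Location is judged by image fusion or direct measurement against that patient's own target volumes. Section 10.1 sends the classification of failures to Appendix A, which gives the event rule: "A failure that intersects the GTV or CTV is classified as a local failure and counts as an event against local control". Appendix A keeps two pattern classes apart from that rule: "Those failures that fall fully within the gross tumor or clinical target volumes (GTV and CTV) are classified as in-volume failures" and "Tumor recurrences classified as out-of-volume must clearly fall outside the planning target volume (PTV"). All others are marginal.

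**The volumes move.** Section 2.5.1 says that patients with RMS and STS "will have further reductions (by 5mm) in their clinical target volume (CTV) margins". Section 12.1 (second phase accrual) describes the cut as 2 to 1.5 cm for Group III RMS and 1.5 to 1.0 cm for Resected STS, and says that second-phase patients in these groups "may be at higher risk for local failure than those in the first phase (due to clinical treatment margin reduction"). The PTV moves too. For PTV1, section 6.3.2.1 has "This volume includes the CTV1 with a treatment site and immobilization device specific margin".

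**The yardsticks do not move.** The targets stay at 85% (Group III RMS) and 90% (Resected STS). Table 12.1.5 monitors the second phase alone and both phases pooled, and "the accrual of patients will be held if the stopping rule is activated by any one of the two monitoring plans".

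**The margins disagree.** Section 6.3 gives CTV margins of 1 cm for RMS (6.3.2.1) and 1.5 cm for STS (6.3.3.2). Section 12.1 gives 1.5 cm and 1.0 cm for the second phase.

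**The concern.** Objective 1.1.2 asks whether greater conformality costs efficacy. The failures that a narrower margin could add lie at or beyond the edge of the new CTV. Those that lie wholly beyond it leave the local-control count, and the boundary of the count moves inward together with the margin. The error can go only one way, towards apparent maintenance of control.

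Monitoring the second phase separately does not remove this, because it uses the same narrower region. The pooled plan combines counts made on two different regions, although it can only add stops to the second-phase rule. Since section 2.1 describes the protocol as nearing complete accrual, what is now at stake is mainly the final estimate and its comparison with the lower limits in section 12.1. The effect on stopping is largely past.

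**Working it through.** **1. The plan's own limits.** For the second phase, section 12.1 gives 5% lower limits of 26/35 (74.3%) and 50/65 (76.9%) at target 85%, and 28/35 (80.0%) and 54/65 (83.1%) at target 90%. Take the smallest k with P(X ≤ k) ≥ 0.05, X binomial at the target rate. This gives 26, 50, 28 and 54, with P(X ≤ k) of 0.069, 0.055, 0.055 and 0.057. The limits reproduce exactly. The question is which recurrences enter the count.

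**2. Which recurrences enter.**

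| Recurrence | 10.1 | Appendix A |
|---|---|---|
| Fully inside CTV | event | event, in-volume |
| Straddles CTV edge | not explicit | event, marginal pattern |
| Outside CTV, not clear of PTV | not an event | not an event, marginal pattern |
| Clearly outside PTV | not an event | not an event, out-of-volume |

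**3. Counted against true control.** Let p be true control with every local recurrence counted, and s the share of all failures that lie wholly outside the CTV. Counted control = 1 − (1 − p)(1 − s). The documents do not give s, so 5%, 10% and 20% are assumptions, as are p = 0.75 (RMS) and 0.80 (STS). I also assume that a patient with an uncounted recurrence stays in the count as controlled. Such a patient goes off study under 13.3.2, and the plan does not say how the count treats this. Example: RMS, s = 0.10, 1 − 0.25 × 0.90 = 0.775.

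Final comparison: P(X ≤ 25) for RMS and P(X ≤ 27) for STS at n = 35. Second-phase stopping: exact recursion over all seven rows of Table 12.1.5, stopping at or below the minimum (RMS 2, 5, 9, 12, 16, 20, 25; STS 2, 6, 10, 14, 18, 22, 27).

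| Group | s | Counted control | Below final limit | Stops in second phase |
|---|---|---|---|---|
| RMS, true 75% | 0 | 75.0% | 0.37 | 0.43 |
| | 5% | 76.3% | 0.31 | 0.37 |
| | 10% | 77.5% | 0.25 | 0.31 |
| | 20% | 80.0% | 0.15 | 0.20 |
| STS, true 80% | 0 | 80.0% | 0.40 | 0.46 |
| | 5% | 81.0% | 0.34 | 0.40 |
| | 10% | 82.0% | 0.29 | 0.34 |
| | 20% | 84.0% | 0.19 | 0.24 |

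These rows cover every failure outside the CTV. They do not isolate the 5 mm cut.

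**4. Precision.** Standard error at n = 35: √(0.75 × 0.25/35) = 7.3 points; √(0.80 × 0.20/35) = 6.8 points.

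**5. At the interim rates.** Section 2.1 reports 2-year control of 89% (RMS) and 94% (STS). With s = 10%: 1 − 0.11 × 0.90 = 90.1% and 1 − 0.06 × 0.90 = 94.6%, shifts of 1.1 and 0.6 points. In patients, 35 × 0.11 × 0.10 ≈ 0.4 and 35 × 0.06 × 0.10 ≈ 0.2. Even with all failures counted, the second-phase rule stops with probability only 0.02 and 0.005.

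**6. What the 5 mm cut can hide.** For a spherical GTV of radius r with no anatomic barrier, the share of CTV volume removed when the margin goes from a to b is 1 − ((r + b)/(r + a))³. For a 5 cm GTV this is 1 − (4.0/4.5)³ = 30% (2 to 1.5 cm) and 1 − (3.5/4.0)³ = 33% (1.5 to 1.0 cm). Over GTVs of 10 down to 3 cm it runs from 20% to 42%. This is volume, not a share of failures. A recurrence centred in the dropped shell lies at most 0.5 cm from the reduced CTV. If it is roughly spherical and at least 1 cm across, its radius is at least 0.5 cm, so it reaches that CTV and counts under Appendix A.

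The PTV gives no fixed boundary either. With a 5 mm set-up margin and a 5 cm GTV, PTV volume falls by 27% and 30%.

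**The case against.** The strongest reply has four parts.

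- **The straddling case is largely settled.** A reader might infer a deep conflict between 10.1 and Appendix A. The text does not support that. Section 10.1 does not require a recurrence to lie fully inside the CTV, it refers to Appendix A, and Appendix A's event rule is explicit. Its fully-within wording defines a pattern class, not the event. What remains is a wording gap in 10.1. This part stands.
- **The 5 mm effect is small.** A reader might take the shell volumes, or the probabilities in the table, as the effect of the cut. Neither is. The intersection rule already captures most sizeable recurrences that start in the shell, and the table covers all failures outside the CTV. Sections 2.6.1.1 and 2.6.1.2 report few marginal failures, though with wider margins. This stands as a limit on size, not as proof of no effect.
- **These failures are not lost.** Patterns of failure belong to the primary objective (1.1.3). Section 10.5 counts any new local disease as progression after complete resection, without a CTV bound, and section 12.1 estimates progression beside local failure. This covers completely resected STS patients well. It does not help Group III RMS, which Appendix D defines by biopsy or partial resection. None of it enters the local-control estimate or Table 12.1.5.
- **The comparison is with a target, and the cut follows national protocols.** No comparison between phases is planned, and section 12.1 calls the targets expected estimates rather than historic rates. The documents do not say whether those targets assume failures bounded by the CTV, so a fixed region is not shown to match them better. It would make the two phases comparable, which is why it belongs beside the planned count and not in its place.

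**Conclusion.** The point holds in limited form, with medium confidence because section 10.6 and the Appendix A figure are not available. On the available text, a recurrence that does not touch the patient's own CTV is not a local-failure event. In Group III RMS and Resected STS the region that counts narrows with the margin while the targets stay fixed, so any bias favours no loss of control.

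The size cannot be known from the documents. Under the assumed shares the shift stays below one standard error at 35 patients, and near the interim rates it is about 1 point or less at a 10% share. The between-phase part is smaller still. The documents do not support the inference that safety monitoring failed or that a real loss of control has been hidden. The point is worth fixing before the final analysis, because the bias has one direction and section 2.1 intends the cohort as a benchmark for later studies.

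**What to change.** (a) State the event rule in 10.1 in the same words as Appendix A, so that a recurrence straddling the CTV edge is classified one way.

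(b) Reconcile the CTV margins in section 12.1 with those in section 6.3. This review does not say which is right. Do this before (c), because the fixed region cannot be drawn until it is settled.

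(c) Keep the CTV-based count. Beside it, report local control, and apply it at any remaining looks, on one region per group that is fixed across phases and not tied to the delivered CTV or PTV. One example, for counting only, is GTV1 plus that group's first-phase CTV margin. Label it as added after interim rates were known, and keep the GTV, CTV and PTV locations for objective 1.1.3.

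The cost is a wording change, one extra count and a little reclassification from locations that 10.1 already has compared with the target volumes. Reported control may be slightly lower, and the added count will have been defined with interim results in view.
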